3. OBJECTIVES AND ENDPOINTS

Primary Objective	Primary Endpoint
To assess safety and tolerability of CX-4945 administered orally twice daily to patients with severe COVID-19	• Adverse Events experienced by patients from randomization to Day 60 (including vital signs, physical findings, clinical laboratory, and ECG results) as characterized by type, frequency, severity (as graded by Common Terminology Criteria for Adverse Events (CTCAE version 5.0), timing, seriousness, and relationship to study therapy.
Secondary Objectives	Secondary Endpoints
• To compare time to clinical recovery in the CX-4945 treatment group evaluated from randomization through Day 28 as compared to the control arm.	• Number of days from randomization to discharge, or alleviation of cough (defined as mild or absent in a patient reported scale of 0=absent, 1=mild, 2=moderate, and 3=severe). Improvement must be sustained for at least 48 hours.
	• Number of days from randomization to normalization of fever (defined as <36.6°C from axillary site, or < 37.2°C from oral site or < 37.8°C from rectal or tympanic site), normalization of respiratory rate (< 24 bpm while breathing room air), resolution of hypoxia (defined as SpO2 ≥ 93% in room air or P/F ≥ 300 mmHg). All these improvements must be sustained for at least 48 hours.
	 Number of days from randomization to the first day on which the subject satisfies one of the following three categories from the ordinal NIAID 8-point Clinical Progression Outcomes scale collected daily from randomization through Day 28:
	Hospitalized, not requiring supplemental oxygen - no longer requires ongoing medical care;
	 Not hospitalized, limitation on activities and/or requiring home oxygen;
	Not hospitalized, no limitations on activities.
To compare changes in clinical status of patients enrolled to CX-4945 treatment arm as	Difference in percentage of subjects with clinical recovery compared at Day 14 and Day 28. Clinical recovery is defined as:

CONFIDENTIAL Page 22 of 66

s. ty	ite, or < 37.2°C from oral site or < 37.8°C from rectal or ympanic site), normalization of respiratory rate (< 24 bpm
a	while breathing room air), resolution of hypoxia (defined as $SpO2 \ge 93\%$ in room air or $P/F \ge 300$ mmHg). All these mprovements must be sustained for at least 48 hours.
Day	centage of participants at each clinical status at Day 14 and 28 assessed by using the ordinal NIAID 8- point Clinical gression Outcomes scale:
1) L	Death;

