	Hospitalized, on invasive mechanical ventilation or acorporeal membrane oxygenation (ECMO);
· · · · · · · · · · · · · · · · · · ·	Hospitalized, on non-invasive ventilation or high flow gen devices;
4) H	Hospitalized, requiring supplemental oxygen;
	Hospitalized, not requiring supplemental oxygen - requiring oing medical care (COVID-19 related or otherwise);
· ·	Hospitalized, not requiring supplemental oxygen - no longer uires ongoing medical care;
	Not hospitalized, limitation on activities and/or requiring ne oxygen;
8) N	ot hospitalized, no limitations on activities
evidence of anti-viral activity of CX-4945 as compared to the Day	Gerence in proportions of patients with conversion of tive RT-PCR to negative RT-PCR as assessed at Day 1, 8, Day 14 and Day 28
	inges in chest imaging from Screening (Day 0)to Day 5 or 14 (if applicable) as defined by:
0]	Number of quadrants/ pulmonary lobes affected

CONFIDENTIAL Page 23 of 66

	 Change in number and/or size of COVID-19 pulmonary lesions (ground-glass opacity, consolidation, mix pattern) assessed by chest CT/X-ray
To evaluate the Clinical Benefit of Silmitasertib (CX-4945) relative to the control arm in patients with Severe COVID-19.	 Days of hospitalization from randomization through Day 28. Days of supplemental oxygen (if applicable) from randomization through Day 28. All-cause mortality status: the number of deaths occurred in each treatment group from randomization through Day 60. Days of non-invasive ventilation/high flow oxygen (if applicable) from randomization through Day 28. Days of invasive mechanical ventilation/ECMO (if applicable) from randomization through Day 28. Number of patients returned to room air after randomization through Day 14 or Day 28. Change in pulse oxygen saturation (SpO2) from randomization to Day 4, 8, 11, 14 and 28. Number of documented venous thromboembolism (VTE), arterial thrombosis (stroke, myocardial infarction, other) and microthrombosis events from randomization through Day 28. Changes in EQ-D5-5L (used as an indicator of symptom improvement) from randomization to Day 8, 14 and 28.
To evaluate changes in inflammatory markers	 Changes in plasma IL-6 level from randomization to Day 4, 8, 11, and 14 Changes in CRP, LDH, CPK, ferritin, D-dimer from randomization to Day 4, 8, 11, and 14

CONFIDENTIAL Page 24 of 66

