5.1.1. Inclusion Criteria

Patients must meet all of the following inclusion criteria to be eligible for enrollment in the study:

- 1. Male or non-pregnant female adult ≥ 18 years of age
- 2. Diagnosed or confirmation of COVID-19 infection by standard RT-PCR assay or equivalent testing within 7 days prior to randomization (Day1).
- 3. Hospitalized patient with severe illness caused by SARS-CoV-2 (**Note:** Prior or current use of remdesivir or dexamethasone (SOC) are allowed under the investigator's discretion. Concomitant treatment with other investigational antiviral drugs or immunomodulators are not permitted from Day1 through Day 28)
 - Symptoms of severe systemic illness/infection with COVID-19:
 - At least 1 of the following: fever, cough, sore throat, malaise, headache, muscle pain, shortness of breath at rest or with exertion, confusion, or symptoms of severe lower respiratory infection including dyspnea at rest or respiratory distress

AND

- Clinical signs indicative of severe systemic illness/infection with COVID-19
 - At least 1 of the following: $RR \ge 30$, $HR \ge 125$, SaO2 < 93% on room air or requires $\ge 2L$ oxygen in order to normalize SaO2.
- 4. Patient (or legally authorized representative) provides written informed consent prior to initiation of any study procedures.
- 5. Adequate hematopoietic capacity, as defined by the following:
 - a. Hemoglobin \geq 9.0 g/dL and not transfusion dependent
 - b. Platelets $> 100,000/\text{mm}^3$
 - c. Absolute neutrophil count $\geq 1500 \text{ cells/mm}^3$

CONFIDENTIAL Page 27 of 66

- 6. Adequate hepatic function, as defined by the following:
 - a. AST and ALT ≤ 2.5 times upper limit of normal (ULN)
 - b. Total bilirubin $\leq 1.5 \text{ x ULN}$
 - c. Albumin $\geq 2.5 \text{ g/dL}$
- 7. Absence of any active or recurring clinically significant hepatic disease and adequate renal function, as defined by the following:
 - a. Renal: calculated creatinine clearance >45 mL/min for patients with abnormal, increased creatinine levels (Cockcroft-Gault formula).
- 8. Ability to take oral medication and be willing to adhere to drug administration and premedication requirements (see **Section 6.3**) throughout study duration.

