8.2.1.3. Vital Signs and Physical Examination

Patients will have a full physical examination to include an examination of all major body systems, height (at screening only), weight, blood pressure and pulse rate, which may be performed by a physician, registered nurse or other qualified health care provider, as acceptable according to local regulation. A symptom-directed physical examination should be limited to systems of primary relevance (i.e., cardiovascular, respiratory, and systems associated with symptoms). Changes from baseline abnormalities should be recorded at each subsequent physical examination. New or worsened abnormalities should be recorded as an adverse event.

Pulse oximetry should be collected prior to collection of the blood pressure, pulse rate, and temperature. Oxygen levels should be evaluated on the finger in accordance with the site standard procedures. All abnormalities will be evaluated by the study physician.

Blood pressure, heart rate, respiration rate, and temperature should be recorded after approximately 5 minutes rest. An abbreviated physical exam is an assessment for emergent toxicities or changes from prior visits and a symptom directed exam conducted by a physician, trained physician's assistant or nurse practitioner, as acceptable according to local regulation.

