8.2.2.3. COVID-19 8-Point Clinical Progression Outcomes Scale

Progression is assessed on COVID-19 8-point ordinal scale collected daily from randomization through Day 28, regardless of discharge or treatment discontinuation status, to adequately capture relevant COVID19 outcomes. Remote data collection methods, such as electronic data collection, phone, and telehealth assessments can be used after patient discharge from the hospital through Day 28 (see **Section 1.3**). The ordinal scale of patient health status ranges from: 1) Death; 2) Hospitalized, on invasive mechanical ventilation or extracorporeal membrane oxygenation (ECMO); 3) Hospitalized, on non-invasive ventilation or high flow oxygen devices; 4) Hospitalized, requiring supplemental oxygen; 5) Hospitalized, not requiring supplemental oxygen - requiring ongoing medical care (COVID-19 related or otherwise); 6) Hospitalized, not requiring supplemental oxygen - no longer requires ongoing medical care; 7) Not hospitalized, limitation on activities and/or requiring home oxygen; 8) Not hospitalized, no limitations on activities.

8.2.2.4. Pulse Oxygen Saturation (SpO2):

Measuring the amount of oxygen-carrying hemoglobin in the blood relative to the amount of hemoglobin not carrying oxygen will be done at the time points described in the Schedule of Activities (see Section 1.3).

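### The SpO2-change endpoint ignores the oxygen being delivered, so a patient weaned to room air can score worse than one escalated to high flow

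*Combined protocol and SAP*

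**What the plan says.** Section 3 (repeated in the synopsis) gives the endpoint as "Change in pulse oxygen saturation (SpO2) from randomization to Day 4, 8, 11, 14 and 28". It sits under the objective "To evaluate the Clinical Benefit of Silmitasertib (CX-4945) relative to the control arm in patients with Severe COVID-19", so it is meant for comparison between arms.

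Two sections describe the measurement. Section 8.2.1.3 says "Oxygen levels should be evaluated on the finger in accordance with the site standard procedures". Section 8.2.2.4 says "Measuring the amount of oxygen-carrying hemoglobin in the blood relative to the amount of hemoglobin not carrying oxygen will be done at the time points" in the schedule. Neither mentions the oxygen being given. The schedule of activities (section 1.3) lists SpO2 with no companion entry for device, flow or FiO2.

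Inclusion criterion 3 (section 5.1.1) offers alternative signs of severity: high respiratory rate, high heart rate, SaO2 below 93% on room air, or a need for at least 2 L of "oxygen in order to normalize SaO2".

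For continuous efficacy data, section 9.8.4.1 names ANCOVA, or a rank-based or other non-parametric method. Section 9.7.2 leaves covariates to a separate SAP, which is not part of the document reviewed.

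Elsewhere the plan does allow for oxygen. Recovery includes "resolution of hypoxia (defined as SpO2 ≥ 93% in room air or P/F ≥ 300 mmHg").

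**The concern.** SpO2 can be read as a measure of lung function only if the oxygen being breathed is known. A patient who enters on oxygen may already have a normal reading, and recovery then shows as needing less oxygen, not necessarily as a higher saturation. Taking oxygen away can lower the reading in someone who is improving; adding it can raise the reading in someone who is deteriorating. A raw change treats the first as harm and the second as benefit.

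The secondary endpoints are there to give a first view of possible clinical benefit while a larger trial is being prepared (section 2.3). With about 20 patients per arm, and no stratification by oxygen support described in section 9.4, the arms could differ in baseline oxygen use by chance. A mean SpO2 change with the wrong sign would mislead even in a purely descriptive table.

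**Working it through.** The plan states no SpO2 mean, standard deviation or target difference, so there is no figure to reproduce. The question is whether the raw change can rank patients or arms wrongly. From the documents I take the 93% room-air threshold, the ordinal categories, and 40 patients randomised 1:1 (section 9.3), hence 20 per arm. All saturations, FiO2 values and patient counts by course below are assumptions.

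**1. Two patients, no FiO2 needed.** Change = later SpO2 − baseline SpO2.
- Weaned: 95% on 2 L, later 93% on room air. Change = 93 − 95 = **−2**. The reading meets the room-air threshold, and the ordinal category moves from 4 to 5 or better.
- Escalated: 92% on 2 L, later 96% on high flow. Change = 96 − 92 = **+4**. The ordinal category worsens from 4 to 3.

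The raw change ranks them the wrong way round, by 6 points.

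**2. The same contrast in SpO2/FiO2**, assuming FiO2 of 0.36 on 4 L/min and 0.60 on high flow, with room air at 0.21.
- Weaned, 96% on 4 L to 94% on room air: raw change −2. Ratio 96/0.36 = 267 to 94/0.21 = 448, a rise of 181.
- Escalated, 96% on 4 L to 96% on high flow: raw change 0. Ratio 267 to 96/0.60 = 160, a fall of 107.

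The directions do not depend on the exact FiO2 values. The first ratio rises for any baseline FiO2 above 96 × 0.21/94 = 0.214. The second falls whenever FiO2 is increased at an unchanged saturation.

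**3. Reversal is not automatic.** A weaned patient going from 95% to 93% (−2) against an escalated patient going from 93% to 90% (−3) is ranked correctly. Taking every pair over three assumed grids of whole-number saturations:

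| Weaned, baseline → later | Escalated, baseline → later | Pairs | Weaned strictly worse |
|---|---|---|---|
| 92–95 → 94–98 | 92–95 → 88–93 | 480 | 1% |
| 92–97 → 93–97 | 92–97 → 90–97 | 1,440 | 30% |
| 93–97 → 93–96 | 90–94 → 92–96 | 500 | 76% |

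**4. Arm means.** Assume arm A does better: 14 weaned, 2 escalated, 4 stable with change 0. Arm B has 8, 8 and 4. Let w and e be the mean changes in weaned and escalated patients.

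Mean A = (14w + 2e)/20 and mean B = (8w + 8e)/20, so A − B = 6(w − e)/20 = 0.3(w − e).

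| w | e | Mean A | Mean B | A − B |
|---|---|---|---|---|
| −2 | +4 | −1.0 | +0.8 | −1.8 |
| −2 | +2 | −1.2 | 0.0 | −1.2 |
| −1 | +2 | −0.5 | +0.4 | −0.9 |
| 0 | 0 | 0.0 | 0.0 | 0.0 |
| +2 | −2 | +1.2 | 0.0 | +1.2 |

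In this set-up the sign is wrong whenever weaned patients change less favourably than escalated ones. The comparison is uninformative when the two changes are equal.

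**The case against.** The strongest reply is that the plan already holds much of the missing information. "Progression is assessed on COVID-19 8-point ordinal scale collected daily from randomization through Day 28", and its categories separate no oxygen, supplemental oxygen, non-invasive or high-flow support, and invasive support. The recovery assessment falls on the same days as this endpoint, and scoring its hypoxia component means knowing whether the reading was on room air, or having a P/F ratio, which itself needs FiO2. Section 9.7 promises listings of all collected data. Oxygen support also has its own endpoints: days on each level of support, and "Number of patients returned to room air after randomization through Day 14 or Day 28". This is one of nine clinical-benefit endpoints in an unpowered 40-patient trial whose primary endpoint is safety, and section 9.8.4 disclaims inferential statistics, although 9.8.4.1 names models. The separate SAP might adjust for oxygen support.

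Much of this stands, and it limits the size of the problem. It does not repair the endpoint. Nothing in the plan links those data to the SpO2 change. Category 4 covers all supplemental oxygen short of high flow, and category 7 does not separate home oxygen from room air after discharge. Recovery can be met by discharge alone, so the hypoxia component need not be scored then. ANCOVA on baseline SpO2 would not help, because baseline SpO2 does not carry the oxygen dose. A later SAP can adjust only for what was recorded, and flow or FiO2 is not scheduled with the reading.

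A reader might infer more: that weaned patients always score worse, that the measure can hardly show benefit at all, or that the final analysis is certain to ignore oxygen. The documents support none of these. Reversal depends on the actual saturations, a rise is meaningful in someone who enters and stays on room air, and the SAP text is not available.

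**Conclusion.** The concern holds in a limited form. As defined, the endpoint is a raw saturation change with no room-air condition and no link to oxygen delivered, in a population whose baseline readings can mix room air and supplemental oxygen. A weaned patient can score worse than an escalated one, and the arm comparison can be uninformative or wrong in sign.

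The frequency cannot be fixed from the documents. The 1% to 76% range and the arm differences of −1.8 to +1.2 points come from assumed values; they show what is possible, not what to expect. The consequence is confined to one exploratory secondary endpoint measured at five visits. The primary safety objective is untouched, and the separate oxygen-support endpoints would be reported beside it.

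**What to change.** Record oxygen device and flow or FiO2 with each scheduled SpO2 reading. State in section 3 and the SAP that the analysed quantity is change in SpO2/FiO2, with room air taken as 0.21, and keep raw SpO2 for listings only.

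If that is declined, the minimum is to present and compare SpO2 by the oxygen-support category already collected each day on the ordinal scale, with a note that category 7 leaves oxygen status after discharge unresolved. This needs no new data.

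The full fix costs a few added case report form fields and some SAP wording. It changes no treatment and no visit. Its drawbacks are that FiO2 is only approximate on low-flow oxygen, and that entries may be missing for remote visits after discharge, which sections 1.3 and 8.1.2 allow. It is a cheap improvement.

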4. STUDY DESIGN

4.1. OVERALL DESIGN

This is a phase II multi-center, randomized, open-label, 2 arm parallel-group controlled interventional prospective study of CX-4945 in patients with severe COVID-19. Up to approximately 40 patients will be enrolled into this study. A screening evaluation will occur within 7 days prior to Day 1. All qualified patients will be randomized at Day 1 in a ratio of 1:1 to one of the following two treatment arms:

- Arm A: SOC*/ best supportive care** in combination with CX-4945 1000 mg BID PO or
- Arm B: SOC*/ best supportive care** alone
- * The standard of care (SOC) is not pre-specified, may vary among patients, and may include agents with anti-viral activity, such as remdesivir, among others. Investigator discretion is to be applied for any established SOC. Active concomitant treatment with other investigational antivirals or immunomodulators are not permitted
- ** Best supportive care is defined as intensive care therapy according to current guidelines, evidence, and best practice, including but not limited to lung protective ventilation, thrombosis prophylaxis, renal replacement therapy when indicated, and access to advanced therapies including extracorporeal membrane oxygenation.

The total duration of the treatment will be 14 days. Patients will be followed up at 28, 45 and 60 days from the start of the treatment. The total duration for each patient in the study (including the screening) will be up to 67 days. For details on randomization see Randomization in **Section 6.1.2.**

4.2. JUSTIFICATION FOR DOSE

CX-4945 will be administered twice a day for up to 14 days. The starting dose will be 1000 mg BID (2000 mg total daily dose). This starting dose is based on three completed Phase I studies where patients were administered CX-4945 following a twice-daily (BID) or four-times-daily (QID) dosing regimen for 21 days followed by 7 days of rest. A total of 12 patients were treated in single agent studies at the 1000 mg bid dose level. Additionally, the safety and tolerability of 28 day continuous dosing of CX-4945 at 1000 mg BID was verified during an ongoing Basal Cell Carcinoma (BCC) study with 12 subjects enrolled to date. In total, approximately 115 patients have been treated with 1000 mg twice daily dosing of CX-4945 in several completed and ongoing studies.

4.3. END OF STUDY DEFINITION

CONFIDENTIAL Page 25 of 66

A participant is considered to have completed the study if he or she has completed the treatment phase and follow-up visits at Day 28, Day 45, and Day 60.

Discontinuation from the study drug does not mean the withdrawal from the study assessments. Subjects who discontinued therapy should remain in the study and continue follow-up for key outcomes. The only reasons for study withdrawal are withdrawal of consent and loss to follow-up.

CONFIDENTIAL Page 26 of 66

5. STUDY POPULATION

This study will enroll up to approximately 40 patients with severe Coronavirus Disease 2019 (COVID-19). All study participants will be identified from the currently hospitalized patients. SOC/Best supportive care alone or in combination with CX-4945 will be given to study subjects.

5.1. PATIENT ELIGIBILITY CRITERIA

This study can fulfill its objectives only if appropriate patients are enrolled. The following eligibility criteria are designed to select patients for whom participation in the study is considered appropriate. All relevant medical and nonmedical conditions should be taken into consideration when deciding whether a particular patient is suitable for this protocol.

5.1.1. Inclusion Criteria

Patients must meet all of the following inclusion criteria to be eligible for enrollment in the study:

- 1. Male or non-pregnant female adult ≥ 18 years of age
- 2. Diagnosed or confirmation of COVID-19 infection by standard RT-PCR assay or equivalent testing within 7 days prior to randomization (Day1).
- 3. Hospitalized patient with severe illness caused by SARS-CoV-2 (**Note:** Prior or current use of remdesivir or dexamethasone (SOC) are allowed under the investigator's discretion. Concomitant treatment with other investigational antiviral drugs or immunomodulators are not permitted from Day1 through Day 28)
 - Symptoms of severe systemic illness/infection with COVID-19:
 - At least 1 of the following: fever, cough, sore throat, malaise, headache, muscle pain, shortness of breath at rest or with exertion, confusion, or symptoms of severe lower respiratory infection including dyspnea at rest or respiratory distress

AND

- Clinical signs indicative of severe systemic illness/infection with COVID-19
 - At least 1 of the following: $RR \ge 30$, $HR \ge 125$, SaO2 < 93% on room air or requires $\ge 2L$ oxygen in order to normalize SaO2.
- 4. Patient (or legally authorized representative) provides written informed consent prior to initiation of any study procedures.
- 5. Adequate hematopoietic capacity, as defined by the following:
 - a. Hemoglobin \geq 9.0 g/dL and not transfusion dependent
 - b. Platelets $> 100,000/\text{mm}^3$
 - c. Absolute neutrophil count $\geq 1500 \text{ cells/mm}^3$

CONFIDENTIAL Page 27 of 66

- 6. Adequate hepatic function, as defined by the following:
 - a. AST and ALT ≤ 2.5 times upper limit of normal (ULN)
 - b. Total bilirubin $\leq 1.5 \text{ x ULN}$
 - c. Albumin $\geq 2.5 \text{ g/dL}$
- 7. Absence of any active or recurring clinically significant hepatic disease and adequate renal function, as defined by the following:
 - a. Renal: calculated creatinine clearance >45 mL/min for patients with abnormal, increased creatinine levels (Cockcroft-Gault formula).
- 8. Ability to take oral medication and be willing to adhere to drug administration and premedication requirements (see **Section 6.3**) throughout study duration.

